## 9.2 Sample Size and Randomization

The target sample size is based on the goals of estimating the rates of feasibility measures (i.e., recruitment, adherence, assessment completion, adverse events and retention rates) to inform the design of a larger efficacy trial. This current pilot study is not designed to assess the effect of the eMMB on any outcome. Thus, we will accrue a total of 31 participants, because this number provides reasonably tight estimates of our parameters of interest. We will be able to estimate these rates within +/- 18% using a two-sided 95% confidence interval, and within 9-15% using a one-sided interval (dependent on the observed proportion). If the recruitment rate is below 50% and the adherence and retention rates are below 70% (i.e., 30% drop-out or non-adherence), a larger study may not be feasible. That is, with an observed retention rate of  $\geq 80\%$  (20% lost to follow-up, target N=25 and lost to follow-up N=6) we can be highly confident that the true rate is at least 68% (the lower limit of a one-sided 95% CI for an observed rate of 80% is 68.2%). An adequate retention rate for Week 2 data will be an indicator that this study is successful and we are ready to proceed to the next phase of study.

Power calculations for a subsequent larger study will be based on clinically meaningful differences between the groups on the primary outcome. The number of participants interviewed (20-31) will be determined when data saturation is

reached. As is conventional for thematic analysis, we will conduct interviews until we think there is enough qualitative data to address issues related to the acceptability of study procedures. The study team's experience leads us to believe that 10-15 interviews from each of the two arms will be sufficient to achieve this objective. Our analyses of differences between cancer type and invasiveness will be for exploratory purposes and therefore data saturation using those variables is not the goal. If unexpected information emerges and our timeline allows, we will consider amending the protocol to recruit additional participants.

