## **9.6 Data Analyses**

This study will provide quantitative data on recruitment, adherence, assessment completion, adverse events and retention rates and qualitative assessment of acceptability to guide future study planning. We will calculate 95% confidence intervals for each of the feasibility measures to determine the range of estimates that are consistent with our data. We will track the number of screened participants, those who are eligible, and the percent who agree to participate. For those not meeting the eligibility criteria, reasons will be summarized. The proportion of participants and corresponding 95% CI for participants who participated in the eMMB and AC sessions and those who completed all assessments will be computed; we will also calculate the frequency of any adverse events and percent of participants who complete the 2w visit to assess retention. We will use one-sample tests of binomial proportions to compare the recruitment, adherence, and retention rates to the hypothesized values of 50%, 70% and 70%, respectively. In exploratory analyses, we will compare participants who are non-adherent or who drop out by demographic characteristics, intervention group, and baseline scores of the measures. We will also investigate any differences in participant recruitment, adherence, assessment

completion, adverse events, and retention rates by surgery type and cancer type to identify an optimal patient population for a future study.

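### Section 9.2 supports N=31 with normal-approximation limits: at its own case of 25/31 retained, the one-sided 95% lower limit is 66.7% (Wilson) or 65.3% (exact), not 68% or more

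*Combined protocol and SAP*

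**What the plan says.** Section 9.2 bases the target of 31 on estimating the feasibility rates, because "this number provides reasonably tight estimates of our parameters of interest". It gives two general precision figures. The first is two-sided: "We will be able to estimate these rates within +/- 18% using a two-sided 95% confidence interval". The second, for a limit on one side only, is a range of 9-15% that varies with the rate observed. It then works one example, for retention. With an observed rate of 80% or more, described as "target N=25 and lost to follow-up N=6", it says "we can be highly confident that the true rate is at least 68" percent. The support offered is that "the lower limit of a one-sided 95% CI for an observed rate of 80% is 68.2" percent.

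Section 1.1 makes adequate retention at week 2 the primary indicator that the study succeeded. For the analysis, Section 9.6 says "We will calculate 95% confidence intervals for each of the feasibility measures" and measures retention as the "percent of participants who complete the 2w visit to assess retention". Neither section names an interval method.

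**The concern.** The Wald limit relies on a normal approximation that is poor when the sample is small and the proportion is far from 50%. For a proportion around 80% to 90% in 31 people, its lower limit tends to lie too close to the observed rate, so the confidence attached to it is overstated. Retention, the primary indicator of success, is planned in that region.

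Precision is the stated reason for N=31, and the retention example is the only worked case. If the example is optimistic, the reader is told that 25 of 31 supports more than it does. Because Section 9.6 leaves the method open, the choice could also be made after the data are seen. That choice can matter one participant above the planned case: at 26/31 some methods put the lower limit above 70% and one does not.

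**Working it through.** **Inputs.** From Section 9.2: n = 31 (both arms together), 25 retained and 6 lost, an observed rate of 80%, one-sided 95% confidence, and the 70% benchmark for retention. The one-sided normal quantile is z = 1.645 and the two-sided quantile is 1.960.

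**1. Reproducing the plan's figures.** The Wald lower limit is p − z·√(p(1−p)/n).

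- At p = 0.80: 0.80 − 1.645·√(0.16/31) = 0.80 − 0.118 = 0.682. This is the printed 68.2%.
- One-sided Wald distance at p = 0.5: 1.645·√(0.25/31) = 0.148. At p = 0.9: 1.645·√(0.09/31) = 0.089. These match the printed 9-15%.
- Two-sided Wald distance at p = 0.5: 1.960·√(0.25/31) = 0.176. This matches the printed 18%.

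The documents do not name Wald, but the inference is firm. At 80% and n = 31, the other variants tried give values between 64.2% and 67.8% (Wald with continuity correction, t quantile, Wilson with and without correction, Agresti-Coull, Jeffreys, exact, and the two-sided Wald limit). None gives 68.2%.

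**2. The same limit by better methods.** An observed 80.0% would be 24.8 of 31, which cannot occur. The plan's own count is 25/31 = 80.65%.

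- Wilson: [p + z²/(2n) − z·√(p(1−p)/n + z²/(4n²))] / (1 + z²/n) = (0.8501 − 0.1246)/1.0873 = 0.667.
- Exact (Clopper-Pearson): the 5% quantile of Beta(25, 7) = 0.653.

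| One-sided 95% lower limit | Wald | Wilson | Exact |
|---|---|---|---|
| 80.0% (exact limit interpolated) | 68.2% | 66.0% | 64.6% |
| 25/31 | 69.0% | 66.7% | 65.3% |
| 26/31 | 73.0% | 70.4% | 69.0% |

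Like for like, Wald is higher by 2.2 points (Wilson) to 3.6 points (exact). Measured against the asserted 68%, the shortfall at 25/31 is 68 − 66.7 = 1.3 points (Wilson) or 68 − 65.3 = 2.7 points (exact).

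**3. A check on the claim from the binomial distribution.** If true retention is 68%, P(X ≥ 25 of 31) = 0.090. So 25/31 supports a rate of at least 68% with exact confidence 1 − 0.090 = 91.0%. The smallest count that reaches 95% is 26/31, where P(X ≥ 26) = 0.039.

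**4. Coverage of the nominal 95% lower limit at n = 31, by exact enumeration.**

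| True rate | Wald | Wilson | Exact |
|---|---|---|---|
| 80% | 89.3% | 96.3% | 96.3% |
| 90% | 83.0% | 96.2% | 96.2% |
| 70% to 90%, lowest | 81.7% | 93.0% | 95.0% |
| 70% to 90%, mean | 90.1% | 96.1% | 97.2% |

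The highest Wald coverage anywhere from 70% to 90% is 94.8%, so it never reaches its stated level there.

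**5. The general precision figures.** For observed counts from 16/31 to 28/31 (about 50% to 90%), the distance down to the one-sided lower limit runs from 12.2 to 14.8 points (Wilson) or 13.5 to 16.3 points (exact). The upper end of 9-15% therefore holds under Wilson, but the 9% end is too small at a rate of 90%. The largest two-sided distance over all counts is 17.6 points (Wilson) or 19.1 points (exact), so the 18% stands under Wilson.

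**The case against.** The strongest reply is that nothing printed is miscalculated, that the method is inferred, and that 91% may fairly be called high confidence; a Jeffreys prior gives a 93.9% posterior probability that the rate is at least 68%. The sentence covers every observed rate of 80% or more, and only the boundary count, 25/31, falls short. It is true that this is a matter of method, not of arithmetic. But the plan rests its confidence on a 95% limit and names 25/31 as its case, and 95% is not reached there.

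A second objection has force. Judged by exact confidence, the Wilson wording of about 67% does not reach 95% either: P(X ≥ 25) at a true 67% is 7.3%, which gives 92.7%. Wilson is justified by coverage close to 95% on average, not by a guarantee at each count. Only exact limits give the guarantee.

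Third, the plan ties 9-15% to the observed proportion without giving a range or restricting it to lower limits. The 50% to 90% range is inferred from the match with Wald. At 31/31 the distance is 8.0 points (Wilson) or 9.2 points (exact), so 9% is not impossible at the extreme. This is the weaker part of the criticism, and stating the range settles it.

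Finally, the planned comparison with 70% is a binomial test, not this limit. That is correct and keeps the consequence small.

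**Conclusion.** The concern holds, as a minor point. Section 9.2 claims 95% support for retention of at least 68% from 25 of 31, and the data in that case give 91.0%. The lower limit should read about 67% (Wilson) or 65% (exact). The lower end of the one-sided 9-15% is also too favourable for a lower limit at a high observed rate.

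The consequences are limited. At 25/31 every method puts the limit below 70%, so no comparison with the benchmark changes there, and N stays at 31. The conclusion assumes simple binomial sampling of 31 participants with both arms pooled, a one-sided 95% level as the plan states, and Wald as the method behind the printed figures. The last is inferred from their exact reproduction.

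**What to change.** Choose one interval method and use it in both sections.

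- **Section 9.2, retention example.** Replace 68% and 68.2% with the limit for 25 of 31 retained: about 67% (Wilson) or about 65% (exact).
- **Section 9.2, one-sided precision.** Replace 9-15% with 12-15% (Wilson) or 13-16% (exact), and say that it refers to a one-sided lower limit at observed rates of about 50% to 90% (16/31 to 28/31).
- **Section 9.2, two-sided precision.** Keep 18% under Wilson; change it to about 19% only if exact limits are chosen.
- **Section 9.6.** Name the same method for the feasibility confidence intervals.

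Wilson needs the fewest edits. Exact is the choice if at least 95% confidence must be guaranteed. The cost is two or three figures and a few words. The stated precision becomes slightly less favourable, and no further participants are needed.

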### **Treatment Assignment Procedures**

Eligible, consented, and enrolled participants will be randomized to eMMB or AC. To control for type of cancer and invasiveness of surgery, randomization will occur within cancer type (uterine or ovarian) and surgery type (laparotomy or robotic). There is not a sample size goal within strata.

Randomization (1:1) lists within each strata will be generated. Study team members who are collecting outcome data will not be informed of group assignment.

### **9.3 Definition of Populations**

We will use the revised CONSORT 2010 guidelines for intention-to-treat (ITT) analysis of randomized control trials in our sample considerations. Those guidelines dropped specific ITT in favor of clear descriptions of exactly who would be (or was) included in the analysis per our specification above. We also took into account considerations for minimizing missing data within the context of ITT specified by White et al. We have incorporated flexible windows for the data collection in our protocol and are allowing for possible randomly missing interim assessments. Therefore the population to whom these pilot findings will be generalizable to will be that represented by the sample meeting our requirements for inclusion in the ITT sample.

### **9.4 Interim Analyses and Stopping Rules**

There are no interim analyses planned for this clinical trial. Summaries of process variables (i.e., recruitment, adherence, data collection, adverse events, retention) will be conducted on a rolling basis as the study progresses. The PI will present data on subject accrual to the Independent Monitoring Committee (IMC). Based on the Cancer Registry at WFBCCC from 2015-2017 an average of 128 patients/year had surgery for uterine or ovarian cancer (73% uterine; 27% ovarian). Therefore, assuming 80% of patients are eligible (n=102), and that we can recruit about 30-50% of those eligible (n= 31-51), we anticipate recruiting 31 participants over approximately 8-16 months (2-4 per month). Fidelity of implementing the interventions will also be evaluated during the study period. If we document fidelity less than 80% during the clinical trial, than interventionists will undergo further training with subsequent re-evaluation demonstrating sufficient fidelity.

Futility analyses for efficacy or safety will not be conducted in this pilot study. SAE's related to the intervention will suspend enrollment and/or the study intervention until

a safety review is convened (either routine or ad hoc) by IMC to determine whether the study intervention should continue per protocol, proceed with caution, be further investigated, discontinued, or be modified and then proceed. If SAEs events are related to the interventions, then the relevant intervention protocol will be modified to avoid adverse events. If the frequency of non-serious adverse events is higher than anticipated or alters the benefit risk ratio as determined by the IMC and PI, the study investigators will also modify the relevant intervention protocol. Two or more specific adverse events among participants will prompt modification of the protocol.

## **9.5 Outcomes**

The study team member collecting outcome data will be masked to the participant's intervention group assignment.

### **9.5.1 Primary Outcome**

The primary study outcome is feasibility (i.e., recruitment, adherence, assessment completion, and retention rates)

### **9.5.2 Secondary Outcomes**

Secondary outcomes include proposed outcomes (i.e., pain [primary outcome - pain interference at week 2], sleep disturbances, psychological distress) for the next phase of study. The Patient Reported Outcomes Measurement Information System (PROMIS) measure of pain of intensity (i.e., How would you rate your pain on average?) is the proposed primary outcome (at 2 weeks) for the future larger clinical trial that will be informed by the current study.

Adverse events and qualitative data will also be collected.

## **9.6 Data Analyses**

This study will provide quantitative data on recruitment, adherence, assessment completion, adverse events and retention rates and qualitative assessment of acceptability to guide future study planning. We will calculate 95% confidence intervals for each of the feasibility measures to determine the range of estimates that are consistent with our data. We will track the number of screened participants, those who are eligible, and the percent who agree to participate. For those not meeting the eligibility criteria, reasons will be summarized. The proportion of participants and corresponding 95% CI for participants who participated in the eMMB and AC sessions and those who completed all assessments will be computed; we will also calculate the frequency of any adverse events and percent of participants who complete the 2w visit to assess retention. We will use one-sample tests of binomial proportions to compare the recruitment, adherence, and retention rates to the hypothesized values of 50%, 70% and 70%, respectively. In exploratory analyses, we will compare participants who are non-adherent or who drop out by demographic characteristics, intervention group, and baseline scores of the measures. We will also investigate any differences in participant recruitment, adherence, assessment

completion, adverse events, and retention rates by surgery type and cancer type to identify an optimal patient population for a future study.

Baseline analyses will include descriptive statistics of pain (i.e., intensity, interference, affective, analgesic use), sleep disturbance (patient-reported), psychological distress, background characteristics (i.e., demographic) and other possible confounding variables (e.g., type of cancer, type of surgery, medications) by intervention group. The distributions of continuous variables will be examined to determine the presence of outliers and whether transformations are necessary for analysis. The primary goal of the statistical analysis of these measures for this Aim will be to estimate standard deviations (SD) for use in future studies. Additional analyses will include fitting mixed ANCOVA models (adjustment for baseline) to model the trajectory of pain (and sleep disturbance and distress) by time and group accounting for the repeated measures on a subject; if any meaningful differences between the groups are found at baseline, we will include them in these models. Analgesic use will be modeled in a similar manner using a GEE model with a logit link. We will also use mixed models to examine the daily actigraphy, pain, and other symptom data by group and time. The purpose of all of these models will be to obtain estimates of the SD of change adjusted for covariates of interest and the within-person correlation of the repeated measures, not to perform formal hypothesis testing. In exploratory models we will examine the impact of adherence to eMMB on changes in the measures, subgroup analysis by surgery type, and we will examine the role of pain self-efficacy as a potential mechanism. The purpose of these analyses will be to estimate SD and within-person correlation by subgroup and with adjustment for mechanisms; no formal hypothesis testing will be done. We will also examine the validity of the patient report for intervention practice by examining the concordance between the self-report of MMB practice and the activity level on the accelerometer.

Interview transcripts will be coded independently by two staff members of the QPRO Core. Twenty-five percent of the transcripts will be coded independently by two separate coders to ensure consistency of code application. Unresolved discrepancies reconciled by a third person. Using thematic analysis, the coded text will be iteratively reviewed and interpreted. The qualitative and quantitative analyses will be evaluated in a mixed-methods framework for consistency and discrepancies to refine the protocol for future studies. For example, if the qualitative interviews indicate that a particular subgroup of patients (e.g., by cancer type, surgery type) perceive greater benefit from the eMMB, then we will perform exploratory subgroup analysis of the quantitative data.

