### **Baseline Assessments**

For participants who have successfully been screened for eligibility and are enrolled into the study, baseline assessments will be performed. The baseline assessment may be completed within two weeks prior to surgery.

- *Assessment Completion/Retention.* Percent completion of planned standard and daily assessments.
- *Pain.* The Patient Reported Outcomes Measurement Information System (PROMIS) measure of pain of intensity (i.e., How would you rate your pain on average?), which has been adapted for assessing pain on a numeric rating scale from 0 (no pain) to 10 (worst imaginable pain) “in the last day,” is the proposed primary outcome (at 2 weeks) for the future larger clinical trial that will be informed by the current study. Patient-reported pain is considered the ‘gold standard’ for pain assessment since pain is a subjective experience and PROMIS is supported by the NCCIH and National Cancer Institute. Pain interference, the affective dimension of pain, and analgesic use will be assessed using 9 patient-reported items. *Pain interference* will also be assessed with a PROMIS measure (6-items). The *affective dimension of pain* will be assessed with one item on a scale from 0 (not bad at all) to 10 (the most unpleasant feeling possible for me). *Analgesic use* in the past 24-hours will be tracked daily for one week before and one week post-surgery (postoperative day 1 to 8; day added since participants may report information from the prior day) and converted to a cumulative analgesic consumption score for analysis (2-items). We will also ask participants if they are taking any analgesic medication postoperatively.
- *Sleep Disturbance* will be assessed with a PROMIS Sleep Disturbance short-form (8-items) adapted for daily use.
- *Psychological Distress.* The PROMIS Depression (8-item) & Anxiety (7-item) adapted short-forms will be used to assess psychological distress “in the last day.”

- *Pain Self-Efficacy* will be assessed with the pain management subscale of the Chronic Pain Self-Efficacy Scale, which has been used postoperatively (5-items).

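### Minor: the section 9.6 outcome models pre-specify neither randomisation factor, admit other covariates by an undefined baseline-difference rule, and give analgesic use a logit GEE that does not suit the cumulative score

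*Combined protocol and SAP*

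**What the plan says.** Section 9.2 (Treatment Assignment Procedures) randomises 1:1 from separate lists within cancer type (uterine, ovarian) and surgery type (laparotomy, robotic). It does not say whether the lists are blocked. Section 9.1 gives the reason for stratifying: to control known influences on outcome.

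Section 9.6 says that the primary goal for the symptom measures is to estimate SDs for future studies, and introduces the models as further analyses. The mixed ANCOVA has the baseline value, time and group. For daily data: "We will also use mixed models to examine the daily actigraphy, pain, and other symptom data by group and time". For analgesics: "Analgesic use will be modeled in a similar manner using a GEE model with a logit link". The models are meant to "obtain estimates of the SD of change adjusted for covariates of interest and the within-person correlation of the repeated measures", with no formal testing. The covariates of interest are not listed.

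The rule for adding covariates is "if any meaningful differences between the groups are found at baseline, we will include them in these models". The baseline description covers symptom scores, demographics and "other possible confounding variables (e.g., type of cancer, type of surgery, medications) by intervention group". Surgery type also appears as an exploratory subgroup: "The purpose of these analyses will be to estimate SD and within-person correlation by subgroup and with adjustment for mechanisms". Cancer type has no unconditional counterpart. If the interviews suggest that some subgroup perceives more benefit, "then we will perform exploratory subgroup analysis of the quantitative data".

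The Baseline Assessments part of section 6.2.2 has daily analgesic use "converted to a cumulative analgesic consumption score for analysis", and separately a question on whether any analgesic is being taken after surgery.

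**The concern.** These models exist to hand a covariate-adjusted SD and a within-person correlation to the next trial, so the plan should fix in advance what the adjustment is for. It fixes the baseline value in the ANCOVA and leaves the rest to an imbalance check whose threshold and candidates are unstated. The two factors judged important enough to stratify on are not guaranteed a place, while variables that differ by chance can enter. Two analysts could report different adjusted SDs from the same data, both within the plan.

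The analgesic problem is one of fit. A cumulative consumption score is not, as described, a binary response or a proportion, and no dichotomy is defined. A logit GEE returns log odds and a working correlation, not the SD of change that section 9.6 gives as the purpose of all these models. If the yes/no item is meant, the plan does not say so, and no model is clearly assigned to the score.

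**Working it through.** The plan gives no figure on this point to reproduce.

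**1. Terms named, model by model (section 9.6)**

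| Model | Terms named | Cancer type or surgery type |
|---|---|---|
| Mixed ANCOVA | baseline value, time, group | not named |
| Daily-data mixed models | group, time | not named |
| Logit GEE | similar to the ANCOVA | not named |
| Exploratory models | adherence, surgery-type subgroup, pain self-efficacy | surgery type only, as a subgroup |

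**2. Chance under the baseline-difference rule**

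Inputs: N = 31 and 1:1 allocation (section 9.2), taken as 15 and 16. The thresholds are assumptions, because none is stated. For a continuous variable with no true difference:

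- SE of the standardised difference = sqrt(1/15 + 1/16) = 0.359
- P(|d| > 0.3) = 2[1 − Φ(0.3/0.359)] = 0.40
- P(|d| > 0.5) = 0.16
- P(|d| > 0.8) = 0.03

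**3. Whether the strata enter by the rule**

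Simulated at n = 31 with 27% ovarian (section 9.4) and 50% laparotomy (assumed), threshold 0.3 SD:

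- Lists in permuted blocks of 4: at least one factor exceeds the threshold in about 7% of runs.
- Unblocked lists: about 69%.

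**4. Size of the effect on the SD**

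- Strata left out: the SD rises by 1/sqrt(1 − R²), where R² is the share of baseline-adjusted variance that the strata explain. For an assumed R² of 0.05, 0.10 and 0.20 this is 1.03, 1.05 and 1.12. A sample size scales with the square, so by 1/0.95 = 1.05 up to 1/0.80 = 1.25, which errs on the large side.
- Sampling error of the SD itself: with 31 − 3 = 28 degrees of freedom, the 95% limits are 0.79 and 1.35 times the estimate. The 3% to 12% above lies inside that.
- Cost of two main effects: relative SE of an SD is about 1/sqrt(2·df). It goes from 1/sqrt(56) = 13.4% to 1/sqrt(52) = 13.9% at n = 31, and from 1/sqrt(44) = 15.1% to 1/sqrt(40) = 15.8% at n = 25.
- Surgery-type subgroup SDs, at an assumed even split of 15 and 16 women with df = n − 3: 1/sqrt(24) = 20.4% and 1/sqrt(26) = 19.6%, against 13.9% for one pooled SD adjusted for both factors.

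**5. Rule against fixed strata**

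Simulated with blocks of 4, strata R² = 0.10, and 17 independent candidate covariates unrelated to outcome (all assumed). Relative sampling error of the residual SD:

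| Threshold | Rule | Fixed strata |
|---|---|---|
| 0.3 SD | 15.6% | 13.9% |
| 0.5 SD | 14.2% | 13.9% |
| 0.8 SD | 13.5% | 13.9% |

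The gain from fixing the terms is small and disappears at the highest threshold.

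**The case against.** The best case for the plan is that this is a pilot, section 9.2 says it is not designed to assess effect, and the adjusted models are supplementary to a stated goal of estimating SDs. Nothing is tested between groups, and on the figures above the existing rule performs about as well as fixed strata except at a low threshold. The word meaningful may also signal clinical judgement rather than a numerical cut-off, in which case the probabilities in step 2 only illustrate. All of this stands, and it is why the point is minor. It does not settle which SD will be reported as adjusted.

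Several stronger readings are tempting, and the documents do not support them:

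- *That section 9.6 ignores the randomisation factors.* It lists both as example confounders in the baseline description and plans SDs by surgery type. Section 9.6 also compares feasibility rates by both. What is missing is a pre-specified model term.
- *That the strata could hardly ever enter by the rule.* That holds only for blocked lists, and section 9.2 does not mention blocking.
- *That section 9.1 excludes the factors from the models* by saying that covariate analysis alone would not be enough. That explains stratifying by design and says nothing about model terms.
- *That a logit link can serve only a yes/no variable.* Proportions and, with a cumulative logit, ordinal scores can also use one. The narrower objection remains: the response is not named, and no SD of change results.
- *That the score has no possible model.* The daily-data mixed models cover pain and other symptoms and do not clearly exclude it.

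**Conclusion.** The point holds, as a minor one. Neither cancer type nor surgery type is a pre-specified term in the main outcome models, the other covariates depend on an open-ended imbalance check, and the logit GEE does not suit the analgesic score that section 6.2.2 prepares for analysis.

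A reader might infer biased SDs or a weakened primary result. Neither follows. The feasibility outcome does not use these models, and omitting the strata inflates the SD slightly instead of biasing it downward. The loss is definition, not validity: the adjusted SD is not fixed in advance, and the SD of change for the analgesic score may not be estimated at all.

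The gaps in wording can be read directly from the text. The sizes rest on assumptions: the 15/16 split, the thresholds, the block size, the 50% laparotomy share, the variance explained by the strata, and independent candidate covariates.

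**What to change.** In section 9.6:

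1. Fit cancer type and surgery type as fixed main effects, with the baseline value, in the repeated-measures models, and state that these are the covariates of interest.
2. Keep the baseline-difference rule only as a labelled sensitivity analysis, with a closed candidate list and a stated threshold.
3. Analyse the cumulative analgesic score as a continuous outcome, transformed if skewed, so that its SD is estimated. Use the logit GEE for the yes/no any-analgesic item, and state how often that item is asked, since a GEE for repeated measures presumes more than one occasion.

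The cost is wording and two degrees of freedom, as in step 4 of the working; no new data are needed. At the 27% ovarian share in section 9.4, about 0.27 × 31 = 8 women would be ovarian, enough for main effects but not for a four-cell interaction.

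A separate wording inconsistency can be reconciled in the same amendment: section 4.3 names cancer type alone as the stratification factor, whereas the Précis, section 3 and section 9.2 name both. Section 9.2 should also say whether the lists are blocked, in a form that does not disclose block size to enrolling staff.
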